Adequacy of sample size: A sample size calculation was done using the G*Power software. An effect size of 0.27, was estimated (conservatively) based on previous research¹⁰³. With equal numbers of subjects in each group, and alpha = 0.05, to provide 85% power to detect a difference in HTC rates at six months controlling for history of testing, sex, and ethnicity, a sample of 118 per group (total N = 236) is required. Based on adherence rates from our test of the original ***PlayForward*** game we assume 80% retention at 6 months. To account for the 20% dropout we will seek to enroll 296 participants.

Randomization: We will use a stratified randomization procedure¹⁰⁴ to assign participants to one of the study arms. Gender, race/ethnicity, and age will be included in the randomization algorithm because these variables have been found to be important predictors of HTC in adolescents¹⁰³. The stratification would be as follows two gender groups (girl vs. boy), two ethnic groups (Hispanic vs. non-Hispanic), three groups for race (White, African-American, Other) and two groups for age – (14, 15, 16 vs. 17 and 18). A block size of 6 will be used for the stratification process.

Treatment conditions: The research staff will orient the participants to the use of either ***PlayTest!*** or the control videogames. Players in both groups will play through an online tutorial demonstrating the mechanics of the game. Each player will use a dedicated device to access their game on the web and a set of headphones that they will use during each gameplay session. The research staff will oversee all gameplay to ensure that participants are playing and to field any questions. The control videogames (**see below**) will be engaging and fun but will be devoid of relevant content.

Assessments: We will assess participant characteristics (demographic), outcomes, and process measures (Table 1). For outcomes, we will collect data on actual HTC and assess a variety of mediators and moderators among teens (e.g., attitudes, intentions, knowledge). To measure actual testing in our participants, we will work with health care professionals at school clinics located on the premises of our partner sites to determine if students who participated in our study subsequently got tested. This data will be collected based on the protocol of the specific clinic, and the participants’ personal health information will be de-identified (including results) before being

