- ⊕ At the end of each month, the facilitator will check the *Student Identification Form* to identify any students that have utilized the school based health center during that month.
 - If a student has used the health center, then the facilitator will record pertinent information on the *Health Center Participation Form* that is on the password protected excel document for the monthly time period in review.
- ⊕ At the end of each month, the facilitator will meet with a member of the play2PREVENT team for approximately 10-15 minutes. During this brief meeting the SBHC facilitator and the play2PREVENT team member will print the *Health Center Participation Form* for the time period at hand and both parties will sign-off on its completeness. The printed sheet will then be placed in the secured lockbox with the USB drive.
- ⊕ Use the 3000z billing code for participants that come in for a STI/HIV test to protect privacy during insurance billing.

Data analysis

Phase 2: Data analyses general considerations: All statistical analyses will be conducted based on the “intent-to-treat” principle, through the use of either SPSS or SAS statistical packages.

Statistical analyses: **Primary outcome:** The primary outcome will be the proportion of participants who engage in HTC within the six-month study period. Rates of HTC among intervention and control participants at six months will be compared using Fisher’s exact test and a 2-sided test at the 0.05 level. **Secondary outcomes:** To address the secondary outcomes we will use repeated measures ANCOVAs (with Bonferroni corrections to account for multiple statistical tests). The models will include attitudes, perceived barriers, perceived norms, intentions, self-efficacy, and knowledge as dependent variables, with study condition as the independent variable, and sex, ethnicity, and history of testing as covariates. **Mediators and moderators:** Data will be collected on potential mediators and moderators and examined using conventional methods¹¹³. Baseline levels of these mediators and moderators will be used in the models to assess whether these variables affect the primary or secondary outcomes. In addition, because these variables might change over time during participation in the study, they will also be considered as time-varying covariates. **Mediators:** Based on our logic model¹¹² that will guide the development of the proposed intervention, we predict that 1) attitudes, 2) perceived barriers, 3)

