
Collection and analysis of the in-game data: We will build on systems we have developed to analyze the data collected by the game software or the in-game data⁹⁸, which will serve as the foundation for analytics system built into the game. Briefly, using Player Game State Data (the traditional save/load data so a player can save their progress and pick up later where they left off) and Activity Logging Data (the relevant time-stamped player

actions during gameplay), we will examine the paths taken and decisions made by each player, documenting their exposure to content and the “learning curve” from the in-game data.

All data collected from the assessments will be entered directly into the secure web-based system, OnCore, Yale’s enterprise-wide clinical research management system. OnCore is a fully integrated system development by Forte, which includes three modules: 1) Clinical research management (CRM); 2) Bio-specimen management (BSM); and 3) Patient registry. This project will utilize the CRM module as the electronic data capture system for all case report form data and to support subject tracking. Data will be entered into the OnCore system either by research staff, or with the more sensitive assessments, by the participant themselves. This method limits data entry-associated errors. Before enrolling participants into the intervention, we will conduct a pilot test with two to three participants to assess acceptability and usability of the game, make changes as needed, and confirm data collection procedures.

New proposed plan for analysis approach due to COVID-19

1. Revise power calculations to ensure that a clinically meaningful effect size for the new primary outcome (attitudes around HTC at 6 months in the full cohort) can be detected.
2. Examine **attitudes** around HTC as primary outcome at 6 months in the full cohort.
3. Examine **intentions** to get tested at 6 months in full cohort.
4. Examine **HTC** at 6 months in smaller cohort of students that were able to reach the full 6 months of the study without being impacted by the pandemic (N=135). This study is not powered to detect a difference at this smaller sample size.

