5. Examine **HTC** at 3 months for a sub-cohort of students who were able to reach that time point without being affected by the pandemic (N=237; the study is powered for this outcome at n=236, but at 6 months). While we technically would be powered at this time-point, we would have cut our time to reach the outcome in half, posing a considerable limitation.
6. Examine attitudes and intentions at 3 months (N=237) (to be used in conjunction w #4 directly above).

New data analysis plan suggestion from study's Data Safety Monitoring Board member

- Use mixed models for the repeated measures analyses of the dimensional outcomes, as they use all available data on an individual and are generally robust to data missing at random. The repeated measures ANOVA approach that is mentioned in the document is meant for complete data and is not flexible in accounting for the correlations within individual.

SECTION II: RESEARCH INVOLVING DRUGS, BIOLOGICS, RADIOTRACERS, PLACEBOS AND DEVICES

If this section (or one of its parts, A or B) is not applicable, check off N/A and delete the rest of the section.

A. RADIOTRACERS

N/A

1. Name of the radiotracer: *Write here*
2. Is the radiotracer FDA approved? YES NO

If NO, an FDA issued IND is required for the investigational use unless RDRC assumes oversight.

3. Check one: IND# *Write here* or RDRC oversight (RDRC approval will be required prior to use)

B. DRUGS/BIOLOGICS

N/A

1. If an **exemption from IND filing requirements is** sought for a clinical investigation of a drug product that is lawfully marketed in the United States, review the following categories and complete the category that applies (*and delete the inapplicable categories*):

Exempt Category 1: The clinical investigation of a drug product that is lawfully marketed in the United States can be exempt from IND regulations if all of the following are yes:

1. The intention of the investigation is NOT to report to the FDA as a well-controlled study in support of a new indication for use or to be used to support any other significant change in the labeling for the drug.	
2. The drug that is undergoing investigation is lawfully marketed as a prescription drug product, and the intention of the investigation is NOT to support a significant change in the advertising for the product.	

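### Meeting a six-month head-count does not show that the three-month HIV testing and counseling (HTC) comparison is powered: N=237 at three months does not inherit the 85% set for 236 at six

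*Combined protocol and SAP*

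**What the plan says.** Section 4 (Phase II, Stage 2, Adequacy of sample size) requires 118 per group, 236 in total, "to provide 85% power to detect a difference in HTC rates at six months controlling for history of testing, sex, and ethnicity". The Data analysis part of Section 4 defines the outcome cumulatively: "The primary outcome will be the proportion of participants who engage in HTC within the six-month study period". It compares the arms by Fisher's "exact test and a 2-sided test at the 0.05 level".

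Section 13 later makes attitudes at six months the primary outcome and moves behaviors to secondary. Its COVID-19 plan then lists two HTC analyses:

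- Item 4 looks at six months in 135 students and says: "This study is not powered to detect a difference at this smaller sample size".
- Item 5 looks at three months in a larger group, described as "N=237; the study is powered for this outcome at n=236, but at 6 months", and adds: "While we technically would be powered at this time-point, we would have cut our time to reach the outcome in half, posing a considerable limitation".

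Item 5 gives no three-month rate, effect size or power. Item 1 calls for revised power calculations only for the attitudes outcome.

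**The concern.** HTC counts any test within the window, so power depends on how many tests accrue in each arm as well as on the number of students. Item 5 matches the number of students and treats the shorter window as a separate drawback. The shorter window is itself what puts the power in doubt.

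HTC was the trial's original question, and item 5 is the only HTC analysis in the revised plan that is called powered. A null three-month result could then be cited as an adequately powered negative finding on testing behavior, which the plan has not established.

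**Working it through.** **Inputs from the documents.** Alpha 0.05, two-sided; 85% power; 118 per group; effect size 0.27 with no metric stated; 80% retention; N=237 at three months; gameplay over four weeks.

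**Inputs assumed.** Six-month control rate p0 of 2% to 30%; 118 control and 119 game students, because no split by arm is given.

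**Step 1: the plan's own figure.** The enrolment step reproduces: 118/0.80 = 147.5, rounded up to 148 per arm, 296 in total. The 118 does not follow from 0.27 on a standard two-arm reading. As a standardized difference, n = 2(1.960 + 1.036)²/0.27² gives 247 per arm, and 118 per arm gives about 55% power. As w or f with one degree of freedom, about 123-124 in total would be enough. The 85% is therefore taken at face value from here on.

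**Step 2: rates implied at six months.** For each p0, solve for the game-arm rate p1 that gives 85% power with 118 per arm:

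power = Φ{[(p1 − p0) − 1.96·s0]/s1}

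Here s0 is the pooled and s1 the unpooled standard error of the difference. For p0 = 10%, p1 = 24.67%: s0 = 0.0493, s1 = 0.0483, and (0.1467 − 0.0966)/0.0483 = 1.036, so power is 85%.

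**Step 3: move to three months at a constant rate.** q = 1 − √(1 − p). For p0 = 10%, q0 = 1 − √0.90 = 5.13% and q1 = 1 − √0.7533 = 13.21%. Then s0 = 0.0375, s1 = 0.0371, and (0.0808 − 0.0735)/0.0371 = 0.19, so power is about 58%. Expected tests fall from 118 × (0.10 + 0.2467) = 41 to 118 × 0.0513 + 119 × 0.1321 = 22.

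Fisher power is the exact sum of binomial probabilities over all rejecting tables, at the same rates.

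| Control, 6 mo | Game, 6 mo | Control / game, 3 mo | Power, normal approx. | Power, Fisher | n per arm for 85% at 3 mo (normal approx.) |
|---|---|---|---|---|---|
| 2% | 11.8% | 1.0% / 6.1% | 56.3% | 43.2% | 236 |
| 5% | 17.2% | 2.5% / 9.0% | 56.8% | 46.4% | 233 |
| 10% | 24.7% | 5.1% / 13.2% | 57.7% | 49.9% | 228 |
| 20% | 37.5% | 10.6% / 21.0% | 59.5% | 54.1% | 219 |
| 30% | 48.9% | 16.3% / 28.5% | 61.6% | 57.9% | 209 |

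Two checks on the Fisher column:

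- At six months the same rates give Fisher power of 81-82%. If the rates are instead chosen so that Fisher itself has 85% at six months, three-month power is about 47-61%.
- The exact two-sided p-value is sensitive to which arm holds the odd student. Repeating the sum with 119 controls and 118 game students gives 54-61%.

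**Step 4: let the effect come early.** Keep controls at a constant rate and let a share s of the six-month difference be present by month 3: q1 = q0 + s(p1 − p0). At a constant rate in both arms, s is only 52-65% (for p0 = 10%, 0.0808/0.1467 = 55%).

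| Share of difference by month 3 | Power, normal approx. (control 2-30%) |
|---|---|
| 70% | 68-74% |
| 80% | 78-83% |
| 90% | 86-89% |
| 100% | 90-93% |

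Reaching 85% needs a share of about 83-89%; reaching 83% needs about 80-85%. If instead both arms have 70% of their tests by month 3, power is about 66-70%, and at 90% it is about 80-81% (control 2-20%).

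**The case against.** The strongest reply is that the plan discloses the problem. Item 5 itself notes that the target belongs to six months, qualifies the claim as technical only, and calls the halved time a considerable limitation. That stands against any suggestion of concealment. It does not rescue the inference, because the caveat leaves the power claim in place alongside the lost time.

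The second reply also has force: the constant rate is not in the documents. Gameplay ends at four weeks, so months 2 to 6 follow the intervention and an early effect is plausible. If the whole difference were present by month 3, power would exceed 85%. A reader might therefore infer too much in saying flatly that the comparison is underpowered, or that 56-62% follows from the plan's own inputs. The plan supplies no control rate and no timing, its 85% does not reproduce from 0.27, and the named Fisher test gives lower figures than the normal approximation. The documents support only that power at three months has not been shown.

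A reader might also want to discount the 237 for dropout. Item 5 defines those students as having reached the three-month point, so a further reduction is not supported.

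Finally, HTC is now secondary. That limits the weight of the point, but nothing else in the plan corrects the statement.

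**Conclusion.** The statement in item 5 is unsupported as written and should be corrected. If 85% at six months is accepted, testing runs at a constant rate and the six-month control rate is 2-30%, three-month power is about 56-62% by the normal approximation and about 43-58% by Fisher's exact test (up to 61% if the odd student is a control). A true effect of the size implied by that 85% would then be missed about four times in ten on the first basis and about half the time on the second. With controls at a constant rate, power stays near or above 85% only if roughly 80-90% or more of the six-month difference has appeared by month 3. That cannot be excluded, so the error lies in the inference from head-count to power and in the missing three-month calculation. The consequence is confined to how a secondary HTC result is described and read.

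**What to change.** In item 5 of the COVID-19 plan:

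1. Delete the clause that calls the three-month comparison technically powered, and the comparison of 237 with 236.
2. State that 236 applies to HTC accrued over six months and that power at three months has not been shown.
3. Either give assumed three-month rates for each arm and the resulting power for the test that will be used, as a range over timing assumptions, or label the analysis exploratory.
4. Report the risk difference with a 95% confidence interval, and state that a non-significant result will not be read as no effect on HTC.

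The cost is a few sentences and a short calculation, with no new participants or data. The downside is a less favorable power statement for a secondary analysis.
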